7.1 Study overview and design

This randomized controlled, 3-arm dietary trial aims to assess the rate and extent of changes in the composition of omega-6 and omega-3 HUFA and their metabolic derivatives in response to marked dietary changes in the nutrient omega-6 LA, in ambulatory overweight premenopausal women. The main trial is divided into two phases: 1) a 4 week ‘baseline phase’, and 2) a 12 week ‘diet phase’. There is also an optional 36 week ‘continuation phase’ for participants receiving diet “B”, as discussed below. During the baseline phase, prior to randomization, eligible subjects will complete 7-day food records. Those who are compliant with the food records and meet other eligibility criteria will undergo a baseline testing battery that includes: 1) blood parameters; 2) muscle and adipose tissue biopsies; 3) body composition assessment; 4) functional satiety assessment; and 5) psychometric testing. Participants will then be randomized to one of 3 healthy and nutritionally complete diets with equivalent macronutrient composition differing only in fatty acid content.

After randomization, participants will receive *all* foods through the NIH Metabolic Kitchen for the duration of the 12-week diet phase (i.e. meal replacement). During the first 4 weeks, the iso-caloric ‘weight maintenance’ phase, participants will be provided with the same amounts of daily food calories as they consumed during the 7-day record collection. During the following 8 week ‘ad libitum’ phase (from 4 to 12 weeks), participants will receive the same diets but will be allowed to eat as many servings of study foods as they desire. After completion of the 12 week diet phase, the full testing battery will be repeated.

At completion of the 12 week diet phase, a subset of participants (those receiving diet ‘B’) will have the option of continuing their study diets for an additional 36 weeks. During this ‘continuation phase’, the diets will be identical to their preceding diets. After 6, 12, 18, 24, and 30 weeks of the continuation phase, subjects will participate in follow-up testing sessions. At completion of the 36-week continuation phase, the complete baseline testing battery will be repeated.

Participants will remain ambulatory throughout the study. Subjects will visit the NIH Metabolic Kitchen daily Monday through Friday to obtain foods, and will be advised to continue their usual medical care and medications throughout the study.

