7.3.2 Screening visit (Baseline Phase Visit 1)

Patients will be invited to come to the OP-9 (Outpatient 9) Multiple Medical Specialties Clinic to obtain informed consent by a member of the investigative team. A limited physical exam with current weight and evaluation of venous access will be performed. A thorough medication history will be obtained with special attention given to drugs that may confound the interpretation of metabolic testing such as psychotropic agents, antiretroviral agents, sympathomimetic amines or beta blockers. An

electrocardiogram and baseline blood work (electrolytes, chronic liver disease work-up, renal function, vitamins, thyroid function, HgbA1C, HIV test), a serum pregnancy test and a urine test to screen for illicit drugs will be obtained. Instructions for completing detailed 7-day food records will be given to participants by a member of the Nutrition Dept staff.

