Urine Laboratory Testing	▲		▲
7-day Food Records	▲	▲	
Medical Exam and Interview	▲	▲	
Eating Questionnaires		▲	
Mood Questionnaires		▲	
Weight, Anthropometrics and Vital Signs	▲	▲	▲
Electrocardiogram (EKG)	▲		
DEXA Scan			▲
Muscle and Adipose Tissue Biopsies			▲
Buffet Meal Test			▲

Baseline phase: 1st Visit

The first visit of the baseline phase is described in detail in Section 7.3.2 Screening Visit.

Baseline phase: 2nd Visit

Participants will return for an outpatient visit about 14 days after Baseline Visit 1. The 7-day food records and the results of the laboratory testing will be reviewed. Questionnaires to evaluate eating, satiety and mood will be administered (see Section 7.6.6). Those who remain eligible will be scheduled for a 3rd baseline visit.

Baseline phase: 3rd Visit

Participants will return for an outpatient visit about 7 to 14 days after the 2nd Visit. If their weight is stable, participants will have additional tests, which will require about 6 hours (Testing procedures are listed in Table 4).

Participants will receive a schedule for the remaining study visits and tests. Participants will then be randomized to 1 of 3 diets as described in Section 7.6.2.

Study Diets

The 3 study diets differ only in the amounts of fatty acids that they contain, as described in Sections 8.2. The diets are designed by NIH Clinical center dietitians to be nutritionally complete. All foods will be provided by the NIH metabolic kitchen. Participants are required to visit the NIH Clinical Center each morning, Monday through Friday, to eat breakfast and to pick up study foods, and to return uneaten food to the kitchen. Participants are also asked to keep a daily log of food and beverage intake.

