We will strive for 100% adherence to study diets and daily visit schedules, but recognize based on previous experience and reviews of literature that this may not be practical or achievable in an ambulatory setting for this length of time. Therefore, to maximize adherence participants are provided with a day of emergency meals to eat during missed days whenever possible. They will also receive group-specific food-based guidance from the nutrition team designed to mimic their diet group if they are unable to pick up study diets for more than one day. Subjects will record/report any non-study foods or beverages throughout the study and this will be analyzed as part of the study diet. Finally, we will measure adherence to study diets using two proxies: (1) the LA content of circulating plasma measured at baseline and 4, 8, and 12 weeks of diet exposure; and (2) the number of days they did not pick up study meals. In a posthoc/exploratory manner, we will test for effect modification of the diet effects based on adherence. If effect modification is evident, we will present the results of the adherent subgroup as a posthoc analysis.

Diet Phase

The sequence of procedures in the Diet Phase is given in Table 5. All time-points are targets, and may be adjusted based on practical considerations.

Table 5: Procedures during the Diet Phase

Diet Phase Testing Visits (12 week phase, Diet Days 1-84)

Procedure	Visit 1 (Day 28)	Visit 2 (Day 56)	Visit 3 (Day 84)
Blood draw	▲	▲	▲
Urine Pregnancy Test	▲	▲	▲
Mood Questionnaires	▲	▲	▲
Weight, Anthropometrics and Vital Signs	▲	▲	▲
DEXA Scan	▲	▲	▲
MRI Scan			▲
Muscle and Adipose Tissue Biopsies			▲
Buffet Meal Test	▲		▲

During the 12 week diet phase participants will visit the NIH outpatient metabolic unit every morning for breakfast (Monday-Friday). Each of these 60 meal visits will last about 20 minutes, for a total of 60 hours. Participants will complete the CPRS questionnaire after breakfast once every 2 weeks, which takes about 10 minutes to complete.

On 2 separate occasions after breakfast, once every 4 weeks on Days 28 and 56, participants will have a testing session lasting about 1.5 hours (Testing procedures are listed in Table 5). Twelve weeks after beginning the diet phase (Day 84), participants will have testing that lasts about 6 hours. They will have a shorter 2 hour testing session 4 and 8 weeks after beginning the diet phase.

Optional Continuation Phase

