8.6 Body Composition

Dual Energy X-ray Absorptiometry (DEXA) SCAN

DEXA will be used to measure body composition using x-rays to non-invasively assess skeletal and soft tissue density. The procedure involves low-level radiation exposure. The expected exposure for a scan is (0.001 rem) or the equivalent of less than one day's exposure to natural background radiation. For more information see Radiation in Section 8.9.

Magnetic Resonance Imaging (MRI) assessment of visceral, liver and cardiac fat

People are at risk for injury from the MRI magnet if they have pacemakers or other electrical devices, brain stimulators, some types of dental implants, aneurysm clips (metal clips on the wall of a large artery), metallic prostheses (including metal pins and rods, heart valves, and cochlear implants), permanent eyeliner, implanted delivery pump, or shrapnel fragments. Welders and metalworkers are also at risk for injury because of possible small metal fragments in the eye of which they may be unaware. Subjects will be screened for these conditions before having any scan, and if any are found, the subject will not receive an MRI scan. It is not known if MRI is completely safe for a developing fetus. Therefore, all women of childbearing potential will have a pregnancy test performed no more than 24 hours before each MRI scan. The scan will not be done if the pregnancy test is positive.

People with fear of confined spaces may become anxious during an MRI. Those with back problems may have back pain or discomfort from lying in the scanner. The noise from the scanner is loud enough to damage hearing, especially in people who already have hearing loss. Everyone having a research MRI scan will be fitted with hearing protection. Subjects will be asked to complete an MRI screening form for each MRI scan.

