8.7 Radiation from DEXA Scans

This research study involves exposure to radiation from the 4 DEXA scans in the main study and 3 additional DEXA scans in the optional continuation phase. This radiation exposure is not required for medical care and is for research purposes only. The amount of radiation the subject will receive in the main study is 0.004 rem, and in continuation phase is an additional 0.003 rem, which are below the guideline of 5 rem per year allowed for research subjects by the NIH Radiation Safety Committee. The average person in the United States receives a radiation exposure of 0.3 rem per year from natural sources, such as the sun, outer space, and the earth's air and soil. If a subject would like more information about radiation a copy of the pamphlet An Introduction to Radiation for NIH Research Subjects will be provided.

While there is no direct evidence that the amount of exposure from participating in this study is harmful, there is indirect evidence it may not be completely safe. There may be a very slight increase in the risk of cancer.

Participants will be instructed to tell the doctor if they have had any radiation exposure in the past year, either from other research studies or from medical tests or care, so the research staff can make sure that the subject will not receive too much radiation. Radiation exposure includes x-rays taken in radiology departments, cardiac catheterization, and fluoroscopy as well as nuclear medicine scans in which radioactive materials were injected into the body.

If a subject is pregnant or breast feeding, she may not participate in this research study. It is best to avoid radiation exposure to unborn or nursing children since they are more sensitive to radiation than adults.

9 Subject Monitoring, adverse event grading and withdrawal

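### No pregnancy test is required at Baseline Visit 3, the visit of the first DEXA scan, the biopsies and randomisation, although every later DEXA visit has one

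*Combined protocol and SAP*

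**What the plan says.** Section 8.7 excludes pregnant and breast-feeding women outright ("If a subject is pregnant or breast feeding, she may not participate in this research study") and gives the radiation sensitivity of unborn and nursing children as the reason for avoiding exposure.

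At screening (Baseline Visit 1, Day 1) Section 7.3.2 states that "a serum pregnancy test and a urine test to screen for illicit drugs will be obtained". Appendix 5 lists a negative serum result among the inclusion items but does not say when it must have been obtained.

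Section 7.1 has an eligibility step before baseline testing: "Those who are compliant with the food records and meet other eligibility criteria will undergo a baseline testing battery". In Section 7.5 this falls at Visit 2 (Day 14), where food records and laboratory results are reviewed and "Those who remain eligible will be scheduled for a 3rd baseline visit". No pregnancy test is listed for that review.

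Visit 3 (Day 21-28) has the first DEXA, the muscle and adipose biopsies and randomisation. The only condition Section 7.5 sets for the Visit 3 tests is stable weight, and it sends the reader to the table for their content: "Testing procedures are listed in Table 4". Table 4 has no pregnancy-test row. Its only urine entry at Visit 3 is "Urine Laboratory Testing", which is not defined. Tables 5 and 6, by contrast, each have a separate row headed "Urine Pregnancy Test".

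Two other provisions bear on this. Section 8.6 states that "all women of childbearing potential will have a pregnancy test performed no more than 24 hours before each MRI scan", but Table 4 lists no MRI. Section 12.5 provides for pregnancy testing before sensitive procedures but leaves it to staff judgement and names no visit.

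**The concern.** The bar in Section 8.7 is only as good as the test that enforces it. At the visit where a woman is first irradiated for research and then randomised, the plan requires no current test. A woman who conceives shortly before or after screening could be scanned, biopsied and randomised while ineligible, with every listed procedure followed. Unless staff choose to test her, the next required test is on Diet Day 28, after four weeks of study diet. What is at stake is fetal exposure that the plan itself says should be avoided, and the randomisation of someone the plan excludes.

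**Working it through.** **Reproducing the plan's scan count.** Section 8.7 gives 4 DEXA scans in the main study and 3 in the continuation phase, 7 in all. The marks in Tables 4, 5 and 6 give 1 + 3 + 3 = 7, which agrees.

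**Matching pregnancy tests to DEXA visits.**

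| DEXA visit | Source | Pregnancy test listed at that visit |
|---|---|---|
| Baseline Visit 3 (Day 21-28) | Table 4 | None |
| Diet Days 28, 56, 84 | Table 5 | Yes, all three |
| Diet Days 168, 252, 336 | Table 6 | Yes, all three |

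Six of the seven DEXA visits have a test. Table 6 is informative in the other direction too: Days 126, 210 and 294 have no DEXA and no pregnancy test. In the diet and continuation phases the test follows the scan exactly, and Baseline Visit 3 is the one exception to the pairing.

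**Age of the last required test at the first DEXA.** Visit 1 is Day 1 and Visit 3 is Day 21-28 (target days, Table 4). 21 − 1 = 20 days; 28 − 1 = 27 days.

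**Interval between required tests.** Assume the diet starts the day after Visit 3. Then screening to Diet Day 28 is 20 + 28 = 48 days at the shortest and 27 + 28 = 55 days at the longest.

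**Expected conceptions in the gap.** The number of women randomised is 84 (Section 7.4). The documents give no pregnancy rate, so I assume 2% to 10% per year as a range. Expected number = women × annual rate × days / 365.

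- Low end: 84 × 0.02 × 20 / 365 = 0.09
- High end: 84 × 0.10 × 27 / 365 = 0.62

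A urine test at Visit 3 would detect fewer than this, because very recent conceptions would still be negative.

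**Effect on the trial's numbers.** Fewer than one expected subject is affected, against a planned diet-phase dropout of about 20 (Section 7.4). Sample size, power and the primary comparison do not change.

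**The case against.** The strongest reply is that a test may be intended but not itemised. Table 4 does not list individual assays: the mandatory serum test at Visit 1 has no row of its own either. The row "Urine Laboratory Testing" is marked at Visit 3, and apart from the drug screen, which has its own row, pregnancy is the only specific urine test the documents name. This reading is possible, and if it is right the defect is an unclear label. It does not settle the matter. The same row is marked at Visit 1, where the pregnancy test is done on serum. Visit 1 also has Section 7.3.2 to specify its tests, whereas Visit 3 has only Table 4.

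A second reply is that Sections 3.3.1 and 7.1 speak of repeating the full baseline battery at end visits that include MRI. That suggests a baseline MRI missing from Table 4, which would bring the 24-hour rule of Section 8.6 into play. Such a scan can only be inferred. Section 16.3 also provides for participants who refuse MRI, so the rule could not protect every woman having the baseline DEXA.

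Third, effective contraception is an inclusion criterion (Section 6.2), and Section 12.5 allows testing before sensitive procedures, which Section 12.4 says include DEXA and biopsy. Both lower the risk. Yet contraception did not stop the plan from scheduling a test at every later DEXA visit, and Section 12.5 is discretionary.

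Fourth, 48-55 days is not unusual here: required tests in the continuation phase are 84 days apart. That is fair, and the interval alone is not the fault. What sets Visit 3 apart is a scan and randomisation with no test at the same visit. It is also true that the documents name no pregnancy hazard from the biopsies, but every scheduled biopsy visit is also a DEXA visit, so a test before the scan covers both.

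What stands is that the absolute risk is small and that one clarifying line might be enough.

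**Conclusion.** The concern holds. As written, no required test enforces the Section 8.7 exclusion in the 20 to 27 days before the first DEXA and randomisation, and Visit 3 is the only one of seven DEXA visits without a scheduled pregnancy test. The expected number of conceptions in the gap is about 0.09 to 0.62 over the whole trial, and it depends on the assumed 2-10% annual rate. The day counts use the protocol's target days, and the 48-55 day interval also assumes the diet starts the day after Visit 3. The dose is about 0.001 rem per scan. This is a modest safety and eligibility-enforcement gap that should be closed because closing it costs almost nothing. It does not bear on the validity of the primary analysis. The remaining uncertainty is whether the undefined urine row at Visit 3 was meant to include the test.

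**What to change.** Add the row "Urine Pregnancy Test" to Table 4 with a mark at Visit 3, and require a negative result before the DEXA, the biopsies and randomisation. If the existing urine laboratory row is meant to include this test, say so explicitly. In Appendix 5, state that the pregnancy criterion is confirmed at Visit 3 as well as at screening. In Section 12.5, make testing mandatory for visits with DEXA or biopsy.

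The cost is one urine dipstick per subject on urine already collected at Visit 3, one table row and two wording changes. It adds no visit and no blood draw.

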9.1 Parameters to be monitored

Participants will be closely monitored for adverse reactions by medically qualified staff during the invasive procedures; including the tissue biopsy procedures, the blood sample collection. Appropriate medical care and treatment will be provided if necessary. Study participants will have daily contact with the metabolic kitchen staff during weekdays and will be encouraged to report any potential adverse reactions to study foods.

During the diet phase and continuation phase, the CPRS will be administered to monitor participants' mood. It is possible that important information may be revealed about the subject that in some cases may benefit from medical intervention. In this case, the patient will be advised to share this information with their doctor for follow-up. Furthermore, with the patient's consent, results from these tests will be forwarded to their physician of choice for follow-up.

Participants will be withdrawn from the study if they do not follow the instructions outlined in the protocol and informed consent form. Non-compliance will be set as a threshold of deviation from the provided diet and will be determined by medically qualified staff. Participants may also, at any time, choose to discontinue their participation from the study.

10. Outcome Measures

10.1 Primary Outcome Measures

- Plasma phospholipid fatty acid composition
- Plasma endocannabinoids derived from PL-AA

10.2 Secondary Outcome Measures

- Muscle and adipose tissue fatty acid composition
- Metabolic derivatives of omega-3 HUFA and omega-6 HUFA in plasma
- Pre- and postprandial endocrine hormones
- 24-hr energy metabolism and substrate utilization
- Self-reported eating behavior, satiety, and affective states
- Functional satiety assessment with buffet-style food array
- Anthropomorphic measures and DEXA scan
- 3T MRI for body composition

11. Statistical Analyses

11.1 Overview

This study is a three-arm dietary intervention trial with a baseline measurement and with repeated measures of the outcome variables over time. The primary aim is to measure the pre- post- changes in our primary outcome variables: %omega-6 in HUFA, 2-AG and AEA. In secondary Aim 1, we will measure the rates of change in our primary outcome variables. Exploratory aims will be directed towards the extent and rates of change in our secondary outcome variables (see Section 10.2) in response to dietary interventions.

11.2 Analysis of Data

Fatty acid concentration data will be examined for homogeneity of variance and normality of distribution, and if necessary transformed to meet this criterion. A probability of 0.05 or lower will be considered significant.

Primary Aim: The sample size was selected to provide adequate power (0.8) to test our Primary Aim, as described in section 11.3. In this Aim we plan to assess the extent of changes in %omega-6 in HUFA; 2-AG and AEA; after 84 days of targeted dietary interventions. To achieve this aim we will treat the data coming from a four-group (control and two treatment groups), pre-post study design. There will be a measurement for all the individuals in the study at randomization and at 84 days. The outcome will be the measurement at 84 days.

Secondary Aim 1: To assess the rate of changes in %omega-6 in HUFA; PL-AA; 2-AG and AEA; PL-EPA; and PL-DHA, we will make use of the repeated measures of the outcome variables measured at baseline, and 28, 56 and 84 days into the diet phase. The goal is to compare the rates of change in these outcome variables over time in the three groups. It is expected that the rates of change will be fastest in Group C (the low LA plus omega-3 HUFA diet group).

Exploratory Aims: Additional exploratory analyses will be performed to further examine the metabolic and clinical effects of dietary interventions by: 1) assessing the extent and rates of change of the *other* metabolic mediators and clinical outcome measures, as detailed in Section 10; 2) examining the association between the changes in blood concentrations of fatty acid precursors (e.g. PL-AA) and their metabolic derivatives (e.g. 2-AG); 3) examining the association between changes in precursor fatty acids and clinical outcome measures; and 4) examining the association between changes in the metabolic derivatives of precursor fatty acids and clinical outcome measures.

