7.4 Study Design

We anticipate that 84 subjects will need to complete the baseline phase and be randomized, with an anticipated dropout of about 20 subjects during the diet phase, in order for 64 subjects to complete the 12-week diet phase. Based on previous NIH Clinical Center dietary protocols with a similar baseline phase, we anticipate that 30 to 55% of enrolled subjects will not complete the baseline phase due to lack of attendance, non-compliance with 7-day food records, and/or discovery of an underlying exclusionary condition during the baseline phase history, physical examination or laboratory testing. Therefore, *up to* 180 subjects will be enrolled in the baseline phase so that a sufficient number of subjects (64) will complete the diet phase.

After completing the baseline phase, 84 subjects will be randomized to 1 of 3 diets (Table 3), to be maintained for 12 consecutive weeks. We anticipate that about 20% of subjects will dropout during the diet phase. Therefore 64 subjects are expected to complete the diet phase.

Table 3: Fatty Acids in 3 Study Diets

Diet Group	omega-6 LA*	omega-3 ALA	omega-6 AA	omega-3 HUFA	%omega-6 in HUFA**
A. Orange	8.00	0.40	0.045	0.045	80
B. Blue	1.00	0.40	0.045	0.045	50
C. Green	1.00	0.40	0.045	0.81	20

*Fatty acid intake as percentages of daily food energy (en%).

** Predicted percentage of omega-6 HUFA in total omega-6 and omega-3 HUFA, via the Lands empirical equation, as detailed in Appendix 2

Please see Section 7.1: Study overview and design and Appendix 1: Study Design Flow Diagram.

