11.3 Estimation of Power and Sample Size

We will use one-way analysis of variance to compare the proportion of %omega-6 in HUFA measured at 12 weeks among three groups. Assuming that the %omega-6 in HUFA will be, on average, 0.8, 0.5 and 0.2 in the three groups at the end of the 12 weeks (as predicted by Lands' empirical equation and the nutrient intake targets), we calculated required sample size at three values of standard deviation: the maximum value of 0.5, at 0.4 and 0.3. These values translate to root mean square standardized effect is calculated as 0.6, 0.75, and 1.0. To detect these effect sizes, at a power of 80% and an alpha of 0.05, we will need either 15 individuals per group ($s = 0.5$), 10 ($s = 0.4$), or 6 ($s = 0.3$).

Fig. 6. Sample Size and Power Curve

12 Human Subjects protection

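### The only primary test that the plan names would run on completers, although section 11.2 promises a Day-84 value for every woman and section 7.4 expects about 20 of 84 to leave

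*Combined protocol and SAP*

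**What the plan says.** For the primary aim, section 11.2 describes a pre-post design and states: "There will be a measurement for all the individuals in the study at randomization and at 84 days". It then fixes the endpoint: "The outcome will be the measurement at 84 days". It names no test. The test appears in section 11.3: "We will use one-way analysis of variance to compare the proportion of %omega-6 in HUFA measured at 12 weeks among three groups", sized "at a power of 80% and an alpha of 0.05".

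Section 7.4 plans 84 randomised women "with an anticipated dropout of about 20 subjects during the diet phase", which leaves 64. Section 3.2 repeats 84 and 64, and section 16.2 stops the study when 64 have finished the diet phase.

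The three primary outcomes (%omega-6 in HUFA, 2-AG and AEA) are also measured between baseline and Day 84. Section 7.6.3 and Table 5 schedule the blood draws, and Secondary Aim 1 in section 11.2 relies on "repeated measures of the outcome variables measured at baseline, and 28, 56 and 84 days".

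No section defines an analysis set, a missing-data method for the primary outcomes or a sensitivity analysis for dropout. The nearest texts are the post hoc adherence analysis in section 7.5 and the reporting of missing psychometric data in section 16.3.

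**The concern.** The sentence in section 11.2 cannot hold alongside section 7.4. Its effect is that the plan never says what happens to roughly a quarter of the randomised women in the primary comparison. A one-way ANOVA of 12-week values answers by default: a woman without a Day-84 value drops out of it, along with everything measured on her earlier.

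Completers are no longer the groups that were randomised. If those who leave one diet differ in their fatty-acid response from those who leave another, the Day-84 contrast mixes the diet effect with the selection. The earlier values could reduce that problem, and they are collected anyway.

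**Working it through.** **1. The plan's own sample size.** Section 11.3 takes these means: "Assuming that the %omega-6 in HUFA will be, on average, 0.8, 0.5 and 0.2 in the three groups". The squared deviations from 0.5 sum to 0.09 + 0 + 0.09 = 0.18. The standardised effect is sqrt(0.18/2)/SD = 0.3/SD. Power comes from the noncentral F distribution with λ = n × 0.18/SD² and 2 and 3(n − 1) degrees of freedom.

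| SD | Effect | Stated n per group | λ | Power at stated n | Power at 64/3 = 21.3 per group |
|---|---|---|---|---|---|
| 0.5 | 0.60 | 15 | 10.8 | 0.817 | 0.938 |
| 0.4 | 0.75 | 10 | 11.25 | 0.817 | 0.993 |
| 0.3 | 1.00 | 6 | 12.0 | 0.805 | >0.999 |

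The stated 15, 10 and 6 reproduce exactly. Loss of power for %omega-6 in HUFA is therefore not the problem; the question is bias.

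**2. Share missing.** 20/84 = 23.8%, leaving 64. Section 7.4 also gives about 20%, which would leave 84 × 0.8 = 67.

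**3. Bias in general.** Let p be the share who leave an arm. The completers' mean differs from the full-arm mean by p × (completers' mean − dropouts' mean). With p = 0.238, gaps of 3, 5, 10 and 15 points give 0.7, 1.2, 2.4 and 3.6 points in that arm. The contrast is biased only by the difference between the arms in this quantity.

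**4. Simulation at the planned contrast.** From the plan: Day-84 means of 80 (A) and 50 (B), and 23.8% dropout. Assumed: SDs of 3.7, 6.1, 7.8 and 8.7 at the four visits, recovered from the pilot confidence intervals in Table 2 as half-width/t × √n (for Week 12, 4.35/2.110 × √18 = 8.7); correlation 0.5 to 0.8; dropout after Day 28 that depends on the Day-28 value.

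| Dropout | Bias of completers' B − A (true −30) |
|---|---|
| Random in both arms | about 0 |
| Same selection in both arms, equal spread | about 0 |
| 23.8% in both; in B higher values leave (log-odds 1 to 2 per SD) | −0.9 to −2.1 |
| 10.7% in A, 36.9% in B; selection in B as above, slope 2 | −2.0 to −3.2 |

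An estimate using baseline and Day 28 of all randomised women was within 0.02 of the truth in every row. Against 30 points, 1 to 2 points is 3 to 7%, and the extreme 3.2 is 11%.

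**5. Which model removes the bias.** A second simulation used a smaller assumed contrast of −5.8 (A flat at 76.3, B falling to 70.5). It assumed Day-84 SDs of 4 and 8, correlation between successive visits of 0.70 to 0.85, about 25% dropout over three intervals, and odds of leaving that change 2.7-fold per SD of the previous value.

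| Estimate | Bias |
|---|---|
| Completers, selection in B only | −1.0 to −1.5 |
| Completers, opposite selection in A | −1.5 to −2.1 |
| Likelihood, baseline included, covariance by diet | about 0 |
| Likelihood, baseline included, common covariance, selection in B only | −0.1 to −0.2 |
| Likelihood on Days 28, 56 and 84 only | −0.3 to −0.7 |

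Baseline matters because dropout in the first interval can depend only on baseline, and a woman who leaves before Day 28 has no other value. Under random dropout the likelihood estimate cut the standard error by 2 to 7%.

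**The case against.** The strongest objection is that nothing in the documents shows dropout differing by diet. Sections 3.3.1 and 7.6.2 say that the diets differ only in added visible oils and that participants are blinded; visits and food provision are the same in every arm. So a reader might infer that diet burden drives dropout, but for A versus B the documents point the other way. This stands. What remains is plausibility. Section 5.2.2B itself predicts diet effects on hunger, satiety and mood. Also, 1 en% LA lies below the lowest US quintile mean in section 8.2 (2.9 en%), so outside food would move values in B more than in A.

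A reader might also infer that the primary contrast is biased by a sixth to a quarter. That comes from dividing 1.0 and 1.5 by 5.8 (17% and 26%). The 5.8 is an assumption, half the pooled pilot fall of 76.3 − 64.7 = 11.6; the plan's contrast is 30. The pilot figures are from erythrocytes, whereas section 10.1 specifies plasma phospholipids. The direction was assumed too: reversed selection would understate the effect.

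The simulated dropout was missing at random by construction, so the likelihood model's success was partly built in. Finally, the ANOVA is named only in the sample-size section, and Secondary Aim 1 does use the interim values. That the primary test leaves them out is inferred from the named method; no other method is offered.

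**Conclusion.** The point holds as an internal contradiction and a gap in the primary analysis. Section 11.2 promises Day-84 values that section 7.4 does not expect, and the only named test would run on about 64 of 84 women without using the dropouts' earlier measurements.

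Bias is possible but not demonstrated: it requires selection that acts differently by diet. Under the assumed selection it is about 1 to 2 points of %omega-6 in HUFA, and 3.2 points when dropout rates also differ sharply. This is small against the planned 30 points and would not reverse that conclusion. For 2-AG and AEA, also primary outcomes, the plan gives no effect size or SD, so no such margin can be claimed.

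Two further inferences are not supported. Not every repeated-measures model removes the bias; one without baseline left part of it. Nor is the model already planned: Secondary Aim 1 compares rates of change and names no model, covariance structure or analysis set.

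**What to change.** 1. Correct the sentence in section 11.2 so that it agrees with the expected dropout, and reconcile about 20 women with about 20% in section 7.4.
2. For %omega-6 in HUFA, 2-AG and AEA, estimate the Day-84 diet differences from a repeated-measures likelihood model with diet by visit. Use baseline and Days 28, 56 and 84, with baseline either as a response or as a covariate interacting with visit. Include all randomised women with available data.
3. Use an unstructured covariance, allowed to differ by diet where feasible. Four visits need 4 × 5/2 = 10 parameters per diet, so 30 in all, with about 21 completers per arm. The SAP should therefore name a common unstructured covariance as the fallback.
4. Keep the Day-84 completers' ANOVA as a sensitivity analysis.

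No extra visits, samples or participants are needed, and Secondary Aim 1 already requires the interim values of these outcomes. The cost is SAP text, including a model that Secondary Aim 1 implies but does not name. The downside is reliance on missing at random given baseline and earlier visits. If leaving depends on values never observed, bias can remain.
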